INVESTIGATIONAL PLAN

Study Title: Cardiogenic SHock Intravascular CooLing TriaL (CHILL-SHOCK)

Principal Investigator: [name]

Co-Investigators:

- [name]
- [name]
- [name]
- [name]
- [name]
- [name]
- [name]
- [name]
- [name]
- [name]
- [name]
- [name] [name], PhD
- [name], APN
- [name]

Sponsor: Investigator initiated with support from ZOLL Circulation, Inc.

Intervention: Therapeutic hypothermia using FDA approved ZOLL Intravascular Temperature Management (IVTMTM) system to achieve core temperature of 32-34° for 24 hours in patients who present with cardiogenic shock.

Manufacturer of Intervention: ZOLL (Chelmsford, MA)

Background

Cardiogenic shock complicates 2-8% of all myocardial infarctions in hospitalized patients and despite advances in revascularization and mechanical support, the mortality rate in these patients can be as high as 50% during the index hospitalization.¹ Cardiogenic shock from alternative causes such as advanced heart failure, acute myopericarditis, stress-induced cardiomyopathy, and acute valvular regurgitation are also associated with significant morbidity and mortality.

Hypothermia, as defined by 32-34° Celsius, has been proposed as a potential adjunctive therapy in patients with cardiogenic shock. The role of mild hypothermia has been well established in out of hospital cardiac arrests due to ventricular tachycardia or ventricular fibrillation for improved neurological outcome.² In fact, the American Heart Association (AHA) guidelines recommend therapeutic hypothermia (Class I recommendation) with targeted temperature of 32°C to 34°C for 12 to 24 hours in patients who suffer out-of-hospital cardiac arrest due to ventricular fibrillation (VF).³ AHA also recommends induced hypothermia for patients after in hospital cardiac arrest due to any initial rhythm or after out-of-hospital cardiac arrest due to pulseless electric activity or asystole. This is a Class IIb recommendation, compared to Class I for out-of-hospital VF arrest.

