5. TTE
6. Blood sample for future research

Endpoints

Primary safety endpoints:

1. Arrhythmia requiring medical therapy or therapy with temporary pacemaker
2. Bleeding requiring transfusions as a direct result of the cooling catheter insertion or secondary to resulting coagulopathy
3. Clinically important bloodstream infection, as confirmed with 2 positive blood cultures, or suspected sepsis in the absence of positive blood cultures with a sequential organ failure assessment (SOFA) score >2
4. Hypokalemia with potassium levels below 3.0mEq/L, not secondary to other identifiable causes

Secondary endpoints:

1. Hemodynamic changes during intervention period – Cardiac output/Cardiac Index, PCWP, SVR, mixed venous oxygen saturation (MVO₂), cardiac power index
2. Cumulative vasopressor and inotrope dose requirements (i.e. number of vasoactive and/or inotropic drugs used)
3. Echocardiographic % change in ejection fraction at 18-24 hours (from baseline)
4. In-hospital all-cause mortality

Procedures

Patients admitted to the Coronary Care unit (CCU) at the University of Chicago will be screened by the study investigators and the cardiology fellow on the CCU rotation. Patients meeting the inclusion criteria, as defined previously, will be identified and randomized after informed consent within 12 hours of presentation. Patients will be randomized to either TH plus standard medical care or to standard medical care alone. A pulmonary artery (PA) catheter will be placed at the bedside or in the Cardiac Cath lab if difficult anatomy is anticipated. As mentioned earlier, placement of a PA catheter is part of the standard of care for management of cardiogenic shock. Currently, patients who are admitted to the University of Chicago CCU with cardiogenic shock routinely undergo placement of PA catheter by the cardiology fellow in the CCU or in the cardiac cath lab. Data from the PA catheter is vital in initiating vasopressors/inotropes, assessing the response to the therapies, and possible need for escalation of therapy (i.e. mechanical support). In this study, patients in each arm will undergo PA catheter placement.

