Laboratory, echocardiographic, and hemodynamic parameters will be obtained for patients prior to randomization, near the end of 24 hour cooling therapy, and after 48-96 hours post-randomization. Core temperature will be measured via either thermal tip at the end of a transurethral urinary catheter or endotracheal temperature probe in intubated patients. Rewarming will be accomplished at 0.3°C per hour until temperature reaches 37°C.

Target Enrollment and Study Duration

In this initial pilot study, we anticipate enrolling 20 patients to the study, 10 randomized to standard medical therapy and 10 patients randomized to standard medical therapy and 24 hours of TH. We anticipate completing enrollment within 6 months.

Statistical Methods

The three-dichotomous primary endpoints will be analyzed using a two-sample independent proportion test or a Fisher's exact test with a Bonferroni method continuity correction for multiple endpoints. Furthermore, numerical secondary endpoints will be presented as either

mean \pm standard deviation or median (interquartile range) based upon the distribution of the data. In addition, all numerical secondary endpoints will be assessed using two independent t tests or Mann-Whitney U test for comparisons. Categorical variables will be tested with chi-square tests of association or Fisher's exact tests. Differences will be considered significant using an alpha value of 0.05 for a two-sided test. Analyses will be performed using STATA MP Version 14 (College Station, TX).

Potential risks and benefits to subjects

A. Benefits:

There is mounting evidence that TH has positive effects on cardiac function. Multiple studies have suggested that TH may offer particular benefit in cardiogenic shock. In this prospective trial, the patients will be randomized to TH or standard medical care using simple randomization. With TH, we expect increased cardiac output, increased contractility, lower SVR, and higher cardiac power index which will lead to improved hemodynamics and potentially decreasing pressor requirements.

B. Risks:

Anticipated adverse events that could possibly occur during the study include, but are not limited to:

1. *Risks associated with TH*
 - a. Shivering
 - b. Arrhythmia
 - c. Coagulopathy with or without clinically significant bleeding
 - d. Hyperglycemia
 - e. Hypothermia
 - f. Electrolyte abnormalities
 - g. Infections
2. *Risks associated with cooling catheter insertion*
 - a. Bleeding
 - b. Infection

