- after treatment of the first 10 subjects (5 in the TH arm and 5 in the control arm)
- at the conclusion of the study

In addition, the DSMB may convene additional meetings if necessary to ensure the ongoing monitoring and safety of the subjects treated with therapeutic hypothermia (TH). A copy of the DSMB charter is located in Appendix 2.

We will collect all treatment emergent and serious unsolicited adverse events during the index hospitalization. A treatment emergent adverse event is any untoward medical occurrence associated with the use of therapeutic hypothermia, whether or not considered related. The DSMB will be informed of expected adverse events, such as shivering, bleeding, and bradycardia, that result in termination of the protocol. Additionally, any unexpected adverse events while undergoing TH will be reported to the DSMB, whether deemed related to TH or not. All adverse event details will be provided to the DSMB prior to the meeting with ample time allowed for analysis. This will include details of the individual adverse events as well as the PI's analysis related to causality, severity and frequency. The DSMB will be responsible for

confirmation of the PI's assessment of all adverse events and final adjudication of all adverse events.

The DSMB will include the following individuals who have agreed to serve on it:

- [name] (University of Chicago Medicine – Section of Cardiology)
- [name] (Inova Health System – Section of Cardiology)
- [name] (University of Chicago Medicine – Section of Cardiology)

Payment to Subjects

Participants will not receive monetary compensation for their participation in this study. The cost of the TH catheters, thermal regulation system and associated monitoring will be part of the study costs and patients will not be charged for these services.

Informed Consent

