Appendix 1 – Schedule of Study Activities

	Baseline	18-24 hours (after randomization)	48-96 hours (after randomization)	30-day Follow-Up	90-day Follow-Up
Informed Consent	X				
Review Medial History	X				
Review Medication History	X				
Height and Weight	X				
Vital Signs ^a	X	X	X		
Echocardiogram (TTE)	X	X	X		
Electrocardiogram (ECG)	X	X	X		
Hemodynamics ^b	X	X	X		
Blood Tests ^c	X	X	X		
Vasoactive Medication Dosing		X			
Potassium (pts randomized to cooling)		Q 4 hours			
Glucose Checks (pts randomized to cooling)		Q 1 hour			
Urine Output	X	X	X		
Randomization	X				
Adverse Events		X	X	X ^d	X ^d

^a blood pressure, heart rate, temperature (bladder or esophageal), respiratory rate

^b RA pressures, RV pressures, PA pressures, pulmonary capillary wedge pressure (PCWP), Fick cardiac output and cardiac index, systemic vascular resistance (SVR), pulmonary vascular resistance (PVR), cardiac power and cardiac power index, mixed venous saturation (MVO2)

^c serum lactate level, basic metabolic panel, hepatic function, coagulation parameters, complete blood count (CBC), arterial blood gas (ABG), and optional blood samples for future research

^d to be completed in clinic, when possible, or by phone

^e items to be charged to research during cooling include: meperidine

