The DSMB will meet (in person or via telephone conference) a minimum of 3 times:

- after treatment of the first 4 subjects (2 in the TH arm and 2 in the control arm)
- after treatment of the first 10 subjects (5 in the TH arm and 5 in the control arm)
- at the conclusion of the study

The DSMB may convene additional meetings if necessary to ensure the ongoing monitoring and safety of the subjects treated with TH.

A quorum of at least two (2) DSMB members needs to be present for a meeting to commence. Members may either be present in person or have the option to phone-in if unable to arrive at the meeting location.

All DSMB members will receive an agenda prior to the meeting. In the event that a DSMB member is unable to attend a meeting, that member will receive minutes, as well as any additional notes, with the opportunity to share any additional thoughts on the distributed information.

5. Grading and Attribution Methods for Adverse Events

Grading Scale

The DSMB and the study team will utilize the Adverse Event Grading Scale provided in Table A. All adverse events will be graded according to this scale, the PI will prepare data regarding adverse events for review by the DSMB prior to meeting, and any additional details will be provided to the DSMB by the PI, as necessary.

Table A – Safety Reporting Definitions

Term	Definition
Adverse Event (AE) Ref: ISO 14155-2011 Ref: MEDDEV 2.7/3 12/2010	
Any untoward medical occurrence, unintended disease or injury, or any untoward clinical signs (including an abnormal laboratory finding) in subjects, users or other persons, whether or not related to the investigational medical device.
 
This definition includes events related to the procedures involved (any procedure in the clinical investigation plan).

Adverse Device Effect (ADE) Ref: ISO 14155-2011 Ref: MEDDEV 2.7/3 12/2010	
Adverse event related to the use of an investigational medical device
 
NOTE 1: This definition includes any adverse event resulting from insufficient or inadequate instructions for use, the deployment, the implantation, the installation, the operation, or any malfunction of the investigational medical device.
 
NOTE 2: This definition includes any event resulting from use error or from intentional misuse of the investigational medical device.

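### The body text and Appendix 1 disagree on how long adverse events are collected, and the only mortality endpoint has no fixed day although 30- and 90-day contacts are already scheduled

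*Combined protocol and SAP*

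**What the plan says.** Four places bear on this point.

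- **Endpoints, Secondary endpoints, item 4.** Mortality is defined as "In-hospital all-cause mortality". No day is attached, and no other mortality endpoint appears.
- **Potential risks and benefits, section D (Data Safety Monitoring Board).** "We will collect all treatment emergent and serious unsolicited adverse events during the index hospitalization". The next sentence reads: "A treatment emergent adverse event is any untoward medical occurrence associated with the use of therapeutic hypothermia, whether or not considered related".
- **Appendix 1, Schedule of Study Activities.** The adverse events row is marked at 18-24 hours, at 48-96 hours, under "30-day Follow-Up" and under the matching 90-day column. Footnote d says the last two are "to be completed in clinic, when possible, or by phone". No other row is marked in those two columns.
- **Appendix 2, Table A.** An adverse event is "Any untoward medical occurrence, unintended disease or injury, or any untoward clinical signs (including an abnormal laboratory finding) in subjects, users or other persons". No causal link to the device is required, and no end date is given. An event that led to death is serious.

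Neither the Endpoints section nor Statistical Methods uses anything from the 30- or 90-day contacts. For context, the Background puts in-hospital mortality after infarction with shock at up to 50%, and the planned size is 10 per arm.

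**The concern.** Two things are at stake.

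The first is operational. Suppose a patient is discharged and has a serious event on day 20. Under section D it falls outside collection; under Appendix 1 it should be picked up at the 30-day contact. Table C attaches a 48-hour FDA reporting time to serious events, and the DSMB is to adjudicate all adverse events, so staff need to know which rule applies. The definition of a treatment-emergent event also refers to the use of hypothermia, which leaves it unclear whether events in control patients qualify.

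The second is interpretive. An in-hospital death count depends both on the risk of dying and on how long the patient is watched. Here the watching stops at discharge, a decision made by a treating team that knows the allocation. The plan has no rule for patients transferred, or discharged to hospice, after randomization, so they would count as survivors. In a trial whose stated purpose is safety, the mortality figure should mean the same for every patient.

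**Working it through.** The plan gives no event-rate, power or length-of-stay calculation, so there is no figure of its own to reproduce. The check is a comparison of the texts, followed by arithmetic on size.

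**1. Adverse event window.** Section D: index stay. Appendix 1: through day 90. For anyone discharged before day 90 these give different answers. The Endpoints section attaches no period to the four primary safety endpoints, so it does not settle the matter.

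**2. Mortality window.** Randomization to discharge, with no fixed day. Contacts at 30 and 90 days exist but feed no endpoint.

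**3. Size of one uncounted death.** With 10 in an arm, 1/10 = 10 percentage points. For example, 5 in-hospital deaths out of 10 (50%) plus one death after discharge but before day 30 gives 6/10 (60%) at day 30. Simple randomization may not give exactly 10 per arm, so this is the value at the planned size.

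**4. Protocol time specific to the hypothermia arm.** Inputs: 24 hours of cooling (Patient Population); rewarming at 0.3°C per hour to 37°C (Procedures).
- From 34°C: (37 − 34)/0.3 = 10.0 h; 24 + 10.0 = 34.0 h.
- From 32°C: (37 − 32)/0.3 = 16.7 h; 24 + 16.7 = 40.7 h.
- Adding the 2-3 h to reach target given in Procedures: 34.0 + 2 = 36.0 h to 40.7 + 3 = 43.7 h.

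Appendix 1 schedules hemodynamics, echocardiography and blood tests at 48-96 h after randomization without limiting them to one arm. These hours therefore do not show a longer stay in the cooled arm.

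**5. What a difference in stay would do, if there were one.** This is an illustration on assumed inputs. Assume the same constant death hazard in both arms, a control stay of L days and a hypothermia stay of L + d days. If control in-hospital mortality is p, hypothermia in-hospital mortality is 1 − (1 − p)^((L + d)/L).
- p = 50%, L = 14, d = 1: 52.4%, an apparent excess of 2.4 points.
- p = 50%, L = 7, d = 5: 69.5%, an apparent excess of 19.5 points.
- p = 25%, same two cases: excess of 1.5 and 13.9 points.

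If the hypothermia stay were shorter, the sign would reverse. At a fixed day from randomization the expected difference is 0 under the same assumptions. Only the 50% has a counterpart in the documents (the upper figure in the Background); L, d and the constant hazard are assumptions.

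**6. Power.** Two-sided Fisher's exact test at 0.05, 10 per arm: 5.5% for 50% v 30%, and 29.5% for 50% v 10%. By the normal approximation, 80% power for 50% v 30% would need 93 per arm. No choice of window makes this a test of mortality.

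**The case against.** A reader might infer that safety follow-up ends at discharge, that discharge depends on arm, and that the mortality comparison is therefore biased. The documents do not support that chain.

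- Appendix 1 itself runs adverse event checks to day 90, so a death after discharge could be captured there as a serious event. What is established is a disagreement between two places, not that follow-up stops at discharge.
- No length of stay, discharge rule or discharge figure is given by arm. The 34-41 hours of cooling and rewarming run alongside shock care and could finish before the 48-96 hour assessment common to both arms. This does not exclude a difference in stay: the start of cooling after randomization is not timed, and the Timing of Data Collection section counts the last assessment from completion of cooling. It does mean that the hours alone prove nothing.
- Mortality is the fourth secondary endpoint. The primary safety endpoints are arrhythmia, bleeding, infection and hypokalemia.
- In-hospital mortality matches the only mortality benchmark in the documents ("the mortality rate in these patients can be as high as 50% during the index hospitalization") and is a reasonable measure for a small pilot of a 24-hour intervention. There is no need to remove it.
- Appendix 1 labels its cooling-only rows, so its adverse events row reads naturally as covering both arms. The ambiguity about controls lies in section D.
- A fixed-day endpoint is not quite free: patients who cannot be reached have unknown status.

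All of these stand, and they limit the point. They do not remove the contradiction or give the mortality endpoint a fixed day.

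**Conclusion.** The contradiction between section D and Appendix 1 is certain and must be reconciled. It is equally clear that mortality has no fixed time point and that the scheduled 30- and 90-day contacts feed no endpoint. Observation time may therefore differ between patients. Whether it differs between arms cannot be determined from the documents, and the 1.5 to 19.5 point range above shows only what assumed differences in stay would do. The size that rests on the plan's own numbers is 10 percentage points per uncounted death in an arm of 10. The gain from a fixed day is a figure that can be interpreted, with the same observation time for both arms; it is not power. This is a modest point that is worth correcting because the correction is cheap and vital status left uncollected may be hard to recover later.

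**What to change.** 1. Reconcile section D with Appendix 1: state one adverse event window, counted from randomization and applied to both arms. Word the treatment-emergent definition so that it covers control patients, in line with Table A.
2. Add a vital-status row at the 30- and 90-day contacts in Appendix 1. Record the date of death or the date last known alive, so that status refers to the fixed day rather than to the day of the call.
3. Add 30-day all-cause mortality from randomization as a secondary endpoint, with 90-day mortality in support, and keep in-hospital mortality beside them.
4. Say in Statistical Methods that mortality is reported descriptively, as counts per arm with the number of patients of unknown status.
5. Write a rule for patients who cannot be reached. One unknown status in an arm of 10 leaves that arm's mortality anywhere between x/10 and (x + 1)/10, which is 10 points; one unknown in each arm leaves the difference uncertain over a range of 20 points (10 in either direction).

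The cost is an amendment, one data item and the rule in step 5. No new visit is needed.

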All patients meeting criteria for cardiogenic shock (defined as systolic blood pressure <90mmHg for at least 30 minutes, Cardiac Index < 2.2 L/min/m², pulmonary capillary wedge pressure (PCWP) ≥ 15mmHg, need for vasopressors, or need for mechanical support to keep systolic blood pressure ≥ 90mmHg) admitted to the University of Chicago Coronary Care Unit (CCU) will be randomized to standard medical therapy or to therapeutic hypothermia (32-34°) for 24 hours plus medical therapy in a non-blinded manner with 1:1 randomization using computer-generated random numbers (simple randomization). The cardiogenic shock may be a result of acute coronary syndromes (STEMI, NSTEMI, or UA), ischemic or non-ischemic cardiomyopathy, myocarditis, hypertrophic cardiomyopathy, stress-induced cardiomyopathy, peripartum cardiomyopathy, or cardiogenic shock in a patient with HF with preserved EF. Patients less than 18 years of age or greater than 89 years of age will be excluded. Patients with

baseline heart rate less than 60 beats per minute, baseline temperatures less than 35°C, recent cardiotomy, history of cardiac transplantation, or those who are pregnant will be excluded.

All patients between the ages of 18 and 89 who meet the criteria for cardiogenic shock in the CCU will be screened. Inclusion and exclusion criteria are listed below.

Inclusion Criteria:

- 1) Cardiogenic shock
 - a) Systolic blood pressure <90mmHg for at least 30 minutes
 - b) Cardiac Index < 2.2 L/min/m²
 - c) Pulmonary capillary wedge pressure (PCWP) ≥ 15mmHg
 - d) Need for central venous access, vasopressors, inotropes and/or mechanical circulatory support (i.e. intra-aortic balloon pump, Impella, ECMO) to maintain systolic blood pressure ≥ 90mmHg
- 2) Etiology of shock
 - a) Acute coronary syndromes (STEMI, NSTEMI, or UA)
 - b) Ischemic or non-ischemic cardiomyopathy
 - c) Myocarditis
 - d) Hypertrophic cardiomyopathy
 - e) Stress-induced cardiomyopathy
 - f) Peripartum cardiomyopathy
 - g) Cardiogenic shock in a patient with HF with preserved EF
- 3) Age ≥ 18 years AND ≤ 89 years
- 4) Admission to the University of Chicago CCU

Exclusion Criteria:

- 1) Baseline heart rate < 60 beats per minute
- 2) Baseline temperatures < 35°C
- 3) Recent cardiotomy
- 4) History of cardiac transplantation
- 5) Current pregnancy
- 6) Contraindication to 9.3 French femoral venous access for placement of intravascular cooling catheter

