- 7) Hospice designation (either currently in hospice or previously enrolled within the past 30 days)

B. Data Collected:

The data elements of interest include, but are not limited to the following:

1. *Patient information*
 - a. Name

- b. Date of birth
- c. Medical record number
- d. Phone number
- e. Primary diagnosis
- f. Relevant social and family history
- g. Previous medical history such as clinic notes, current medications, results of all tests, procedures and laboratory assessments.
- h. Medications
- i. Weight and height

2. *Transthoracic echocardiogram (TTE)*
3. *Hemodynamics via pulmonary artery catheter*
 - a. RA pressures
 - b. RV pressures
 - c. PA pressures
 - d. Pulmonary capillary wedge pressure (PCWP)
 - e. Fick cardiac output and cardiac index
 - f. Systemic vascular resistance (SVR)
 - g. Pulmonary vascular resistance (PVR)
 - h. Cardiac power and cardiac power index
 - i. Mixed venous saturation (MVO₂)
4. *Metabolic parameters*
 - a. Serum lactate level
 - b. Basic metabolic panel - Renal function and serum electrolytes
 - c. Hepatic function
 - d. Coagulation parameters
 - e. Complete blood count (CBC)
 - f. Arterial blood gas (ABG)
5. *Physiologic parameters and vital signs*
 - a. Urine output
 - b. Blood pressure
 - c. Heart rate
 - d. Bladder or esophageal temperature
 - e. Respiratory rate
6. *Electrocardiogram*
7. *Vasoactive medication requirements*
 - a. Cumulative inotrope (i.e. milrinone, dobutamine) and vasopressor (i.e. norepinephrine, phenylephrine, dopamine, vasopressin) doses
8. *Blood samples for future research*
 - a. Stored without identifying information for future research, which may include genetic testing

- b. May be shared with outside collaborators for research purposes, with identifiers removed

C. Timing of Data Collection:

Baseline parameters (prior to initiation of cooling):

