administration of medications or a dialysis catheter for temporary dialysis. After successful insertion of the cooling catheter, it will be connected to the Thermogard XP® thermal regulation system. The Quattro® catheter functions as both a central venous triple lumen catheter as well as a cooling catheter. Cooling is achieved by circulating normal saline in a closed system through the catheter. The flow and temperature (range 4°C to 42°C) of the circulating saline serves as the heat exchange mechanism and is controlled by the external Thermoguard® thermal regulation system. The temperature is measured and adjustments are made by the thermal regulation system to automatically maintain target temperature. The target temperature is achieved within 2-3 hours of initiation of TH. Rewarming is accomplished using the same balloon catheter system and heat exchange occurs without infusion of any saline or fluids into the patient. In clinical trials, intravenous catheter based cooling system has been shown to achieve target temperature faster and maintain target temperature with more precision.^{12,14,15}

Medical therapy in both intervention and non-intervention groups will be based on the current recommendations for management of cardiogenic shock. This includes inotropic therapy (i.e. dobutamine or milrinone) for cardiac support, vasopressor therapy (i.e. norepinephrine, dopamine, phenylephrine, epinephrine) to achieve target blood pressure (mean arterial blood pressure \geq 60 mmHg), diuretics for volume removal, and mechanical circulatory support as clinically indicated. All patients included in this study will have pulmonary artery (PA) catheters inserted within 12 hours of randomization via either the internal jugular or femoral venous approach to monitor real-time hemodynamics. The clinicians in the CCU will use the data from PA catheters (cardiac output, mixed venous saturation, systemic vascular resistance, etc.) to guide therapy for both the intervention and non-intervention groups. The primary investigator of this study ([name]) will have no role in the clinical management of the patients.

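### The plan contradicts itself on when the PA catheter goes in, so the first cardiac index and PCWP can be read after the open-label arm is known

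*Combined protocol and SAP*

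**What the plan says.** **Entry criteria.** Under Inclusion Criteria, item 1 (cardiogenic shock) lists 1b, "Cardiac Index < 2.2 L/min/m²", and 1c, "c) Pulmonary capillary wedge pressure (PCWP) ≥ 15mmHg". Items 1a to 1d carry no connecting word. The narrative definition under Patient Population is a comma-separated series that ends "need for vasopressors, or need for mechanical support to keep systolic blood pressure ≥ 90mmHg".

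**Source of the readings.** Data Collected, item 3, places PCWP and Fick cardiac index under "Hemodynamics via pulmonary artery catheter".

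**Allocation.** Patient Population describes non-blinded, 1:1, simple randomization.

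**Order of events.** Procedures states: "Patients meeting the inclusion criteria, as defined previously, will be identified and randomized after informed consent within 12 hours of presentation". Catheter placement is described next, with the remark that both arms receive one and that it is usual care for these patients in this unit. Cooling comes after that. The medical-therapy paragraph of the same section adds: "All patients included in this study will have pulmonary artery (PA) catheters inserted within 12 hours of randomization".

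**Baseline.** The last paragraph of Procedures puts the first hemodynamic assessment before randomization. Timing of Data Collection puts it before cooling and does not mention randomization. Appendix 1 shows hemodynamics and randomization in one Baseline column, without an order.

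**Analysis.** Statistical Methods defines no analysis set and gives no rule for a randomized patient later found not to meet a criterion.

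**The concern.** In an open-label trial, eligibility and baseline should be fixed before anyone knows the arm. Here a site can comply with the catheter wording in Procedures and still have no CI or PCWP at the moment of allocation. Two things are then exposed.

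First, secondary endpoint 1 is hemodynamic change, and change needs a baseline. A baseline taken after an open allocation may already reflect treatment given in the knowledge of the arm. In the control arm, a baseline tied to the start of cooling has no time anchor at all.

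Second, if 1b and 1c are mandatory, a patient can be randomized and only afterwards be found outside a threshold. What happens next would be decided ad hoc, with the arm known, because the plan has no rule for it. In a trial of 10 per arm, each such decision carries weight.

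**Working it through.** The plan gives no design figure on this point to reproduce. The check compares its statements and adds some simple arithmetic.

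**1. What each statement implies for the first CI and PCWP**

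| Place | Timing stated | Can the reading follow allocation? |
|---|---|---|
| Procedures, first paragraph | Patients who meet the criteria are randomized; the catheter is described next | Yes, unless a catheter is already in place |
| Procedures, medical-therapy paragraph | Catheter within 12 h of randomization | Yes; an earlier catheter also fits |
| Procedures, last paragraph | Hemodynamics before randomization | No |
| Timing of Data Collection | Before cooling | Yes |
| Appendix 1 | Same Baseline column as randomization | Not determined |

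For a patient without a catheter at randomization, the last paragraph of Procedures cannot be satisfied together with the order given earlier in that section.

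**2. Largest delays the wording permits**

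- Presentation to randomization: up to 12 h. Randomization to catheter: up to 12 h. Presentation to first reading: 12 + 12 = 24 h.
- If the catheter goes in at 12 h and cooling follows at once, the Appendix 1 visit at 18-24 h after randomization falls 18 − 12 = 6 h to 24 − 12 = 12 h after cooling starts. Timing of Data Collection sets that assessment at 18-24 h after cooling starts.

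**3. Do the readings decide eligibility?**

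- If 1a to 1d must all be met: yes, 1b and 1c are required.
- If any one is enough: no. A patient can qualify on blood pressure or on need for support, without a catheter.
- The narrative contains an or, but that word could join the whole series or only its last two items. The numbered list does not settle it.

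**4. Illustration, if all criteria are required**

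Let n be the number randomized without a catheter in place and f the share of them who miss 1b or 1c at first reading. The documents give neither, so both are assumptions. Expected number = n × f; chance of at least one = 1 − (1 − f)^n.

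| f | n = 20: expected | n = 20: chance of at least one | n = 10: expected | n = 10: chance of at least one |
|---|---|---|---|---|
| 5% | 1 | 1 − 0.95^20 = 64% | 0.5 | 1 − 0.95^10 = 40% |
| 10% | 2 | 1 − 0.90^20 = 88% | 1 | 1 − 0.90^10 = 65% |
| 20% | 4 | 1 − 0.80^20 = 99% | 2 | 1 − 0.80^10 = 89% |

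n = 20 is the upper limit, where nobody has a catheter at randomization. n = 10 assumes that half already do. If such a patient were removed, the arm would lose 1/10 = 10% of its planned size; the plan neither provides for removal nor forbids it.

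**The case against.** The strongest reply is that the plan already intends the right order. It randomizes patients who meet the criteria, and it asks for hemodynamics before randomization. The 12-hour wording does not say after, so a catheter already in place fits it. That sentence concerns monitoring to guide therapy and not screening, and the plan calls the catheter usual care. The or in the narrative definition may mean that no catheter reading is needed for entry.

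Much of this stands, and it rules out three stronger readings.

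- A reader might infer that eligibility is settled after allocation. The documents do not say so: the wording permits a late catheter but does not schedule one, and 1b and 1c may not be mandatory.
- A reader might infer that hypothermia patients would be removed more often than controls, because only they face an added procedure. Nothing in the plan provides for removal on catheter readings, so this is conjecture.
- A reader might infer that patients are cooled before shock is confirmed hemodynamically. Procedures puts the catheter before cooling, and Timing of Data Collection requires baseline hemodynamics before cooling.

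What the reply does not remove is the conflict. The statement that hemodynamics come before randomization does not override the other two. Even if any one criterion is enough for entry, the baseline for secondary endpoint 1 can still be taken after the arm is known.

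**Conclusion.** The concern holds as an internal contradiction on catheter timing. In a non-blinded trial, it lets the first CI and PCWP be taken up to 12 hours after allocation. The effect on the baseline for secondary endpoint 1 does not depend on how 1a to 1d combine. The effect on eligibility arises only if all of them are required, and the plan does not say.

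The number of patients affected is unknown. The illustrative 0.5 to 4 expected patients rest on assumed failure shares of 5-20% and on 10 to 20 patients without a catheter at randomization; with fewer such patients, the figures fall. No bias in a particular direction has been shown.

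This is a 20-patient pilot with safety endpoints as primary, and its own text already contains the better order. The point should be corrected, but it is not serious enough to be a condition for the trial to proceed.

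**What to change.** 1. Reconcile the first and medical-therapy paragraphs of Procedures, and Timing of Data Collection, with the last paragraph of Procedures. Baseline CI and PCWP, and any catheter reading used for eligibility, should be recorded with a time stamp before allocation is revealed, within the existing 12-hour window from presentation. Show the same order in Appendix 1.
2. State whether 1a to 1d are joined by and or by or, in the narrative and in the list alike. Which one applies is for the sponsor to decide.
3. Add to Statistical Methods that every randomized patient is analysed in the assigned arm and that nobody is removed because of later hemodynamic readings.

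**Cost.** Wording only. The plan calls the catheter usual care and places it in both arms, so no procedure is added. The price is that randomization waits for the catheter in patients who do not already have one.
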